3.0 Confidentiality of Data
1. To maintain the confidentiality of the data:
I will use a unique study identifier to code individuals' identifiable data and will store the master list separate from the study data.
\square I will use a unique study identifier to code individuals' data, but it will never be linked to a master list.
☐ Other- please explain: Click here to enter text.
Provide a plan to maintain or destroy identifiers once analysis of identifiable information is complete. Once all data collection is complete and results are posted to ClinicalTrials.gov, we will delete all identifying information collected. This will include downloading all de-identified data from REDCap and storing in an encrypted Box folde I attest that any recordings (audio or video) saved to a portable device will be deleted by formatting the device's storage memory.
How are you storing your electronic data?
□ CWRU Redcap
☐ CWRU Secure Research Environment (SRE)
⊠ CWRU Box
□ OnCore
☐ CWRU Secure Network Drive
☐ Zoom Cloud
☐ Portable device (must be encrypted, not just password protected)

HRP- 503SBER	TEMPLATE: CWRU SBER Protocol		ol
Approved:	09/2021	Prior Version:	05/2021

☑ Other - List storage method and provide justification: *Click here to enter text*.

Please note: if you're storing or entering your electronic data in any system other than an approved system listed above, please contact the CWRU IRB ([contact]).

- I acknowledge that paper research data and documents will be stored in a double-locked secure environment in the following location: Click here to enter text.
 ☑ We will not have paper research documents.
- 3. Will data be shared?

⊠ Yes

- List the exact data elements that will be shared: Data will be shared for the purpose of transcription, where we will send audio files to a third party. We will also share the names of participants enrolled in the research study with KINDER facilitators, who are not study team members. This is because facilitators will be asked to complete a call log and share attendance data for caregivers who are enrolled in the research study, and so will need to be able to distinguish between study participants and those caregivers who are attending KINDER without participating in the study..
- Describe how data will be sent: Audiofiles will be uploaded to GMR
 Transcription services using their secure portal. Transcribed text documents will
 be emailed to the PI. Facilitators will receive an email with the names of study
 participants in a password protected Excel file.

□ No□ N/A

If sharing data, please complete a request to ensure the proper contracts/agreements are in place: https://case.edu/research/faculty-staff/technology-transfer/material-transfer-data-use-agreements

18.0 HIPAA Authorization

Does this study collect, access, use, or distribute any Protected Health Information (PHI)?

Protected Health Information (PHI) is (1) any individually identifiable health information transmitted or maintained in a medical record, paper or electronic, or (2) designated data set that was created, disclosed, or used in the course of providing a health care service such as diagnosis, payment or treatment.

Yes No

□ Yes	⊠ No
If yes, indic	eate how HIPAA authorization will be obtained (check all that apply):
	HIPAA authorization is in the consent form
	I am receiving a Limited Data Set under a Data Use Agreement (DUA)
	Requesting a full or partial waiver of HIPAA for prescreening
	☐ I will complete the Request for Waiver of HIPAA Authorization form. See SpartaIRB Library
□ I	Requesting a full or partial waiver of HIPAA

HRP- 503SBER	TEMPLATE: CWR	U SBER Protoc	ol
Approved:	09/2021	Prior Version:	05/2021

☐ I will complete the Request for Waiver of HIPAA Authorization form. *See SpartaIRB Library*

19.0 FERPA Authorization

Does this study collect, access, use, or distribute any personally identifiable information from student records or personal education information from an education program (defined as: any program principally engaged in the provision of education, including, but not limited to, early childhood education, elementary and secondary education, postsecondary education, special education, job training, career and technical education, and adult education)? This includes, but is not limited to, classroom assignments and course evaluations.

□ Yes	⊠ No
-------	------

If yes, how do you plan to get written authorization from the student (or parent if the student is a minor)?

□ I	will incorpo	orate FERPA	language* int	o the	consent and	obtain	written a	nd dated
signa	iture or auth	orized electro	onic signature	using	g REDCap			

☐ I will incorporate FERPA language* into a separate form and obtain written and dated signature or authorized electronic signature using REDCap

20.0 Risks to Research Participants

1. List the reasonably foreseeable risks such as breach of confidentiality, discomforts, hazards, or inconveniences to the research participants related to their participation in the research. Include a description of the probability, magnitude, duration, and reversibility of the risks. Include the physical psychological, social, legal, and economic risks. Breach of confidentiality. There is small probability that data confidentiality could be breached, such that others outside the study team could connect participant identifying information with study data. Given the sensitive nature of the data collected, which could be potentially embarrassing, we consider this a moderate risk which would be irreversible. It is also possible that other caregivers could share information from group discussion sessions with others. This scenario is slightly more likely than study data being breached, however may be less harmful as caregivers can choose what they share with others during sessions. Report to Adult Protective Services. In rare cases, we may be required to contact Adult Protective Services if we perceive there to be a risk of harm to the participant or the person for whom they provide care. In some cases, we may contact the caregiver encourage them to submit a report to Adult Protective Services if we believe their or their loved one's safety is at risk. This process could be quite stressful for family caregivers, who may also experience adverse effects of stigma from this process. In very rare cases, legal consequences may occur if APS finds evidence of mistreatment. The study team's intention with reporting cases of mistreatment is to protect vulnerable older adults and help care partners connect to critical services if needed. Negative emotions. Some participants may experience discomfort, such as embarrassment or guilt, when answering questions their caregiving relationship or

^{*} FERPA language: 1. Specify the educational records that may be both accessed and used in the research. 2. State the purpose of the access and use of records. 3. Identify to whom the records disclosure may be made.

HRP- 503SBER	TEMPLATE: CWRU SBER Protocol		ol
Approved:	09/2021	Prior Version:	05/2021

participant in KINDER program activities. The likelihood and severity of this risk will vary from person-to-person. We provide resources to family caregivers who experience negative emotions throughout the intervention program and in the consent form.

- If applicable, indicate which experimental procedures may have risks to the research participants that are currently unforeseeable. Click here to enter text.
 N/A
- 3. If applicable, describe the risks to others who are not research participants. There is a very small chance that, should Adult Protective Services be contacted by the study team, the older adult living with dementia (care recipient) may lose their family caregiver if APS finds indications of mistreatment. This would be a severe outcome, but also a potential benefit if care being provided placed the care recipient at risk of harm.
 □ N/A
- Describe the availability of medical or psychological resources that research participants might need. Click here to enter text.
 □ N/A

21.0 Provisions to Protect the Privacy Interests of Research Participants Directions: Indicate the measures that will be taken to protect research participants' privacy interests. Select all that apply:

- ☐ In person interactions will be conducted in a private space where conversations would not be overheard by others -- this could be at a specific location determined by the research team or at a location that the participant chooses.
- ⊠ For online/remote data collection, participants will be advised to choose a location that would be private.
- ☐ Researchers will only contact participants if permission has been given to do so.
- ☑ Other: When participants join the KINDER discussion sessions by Zoom, they will be reminded to keep information they learn about other caregivers private. Access to survey data will be limited to qualified study team members. The study key will only be accessible to the PI. (The PI will therefore be responsible to sending participant online surveys, since these are connected using participant email addresses in REDCap.)

22.0 Potential Benefit to Research Participants

- ☐ There is potential benefit to research participants.

 Describe the potential benefits that individual research participants may experience from taking part in the research. Include the probability, magnitude, and duration of the
 - taking part in the research. Include the probability, magnitude, and duration of the potential benefits. *Do not list compensation*. Click here to enter text.
- oxtimes There is $\underline{\mathbf{no}}$ direct benefit to research participants.

If no direct benefit, state the potential benefit to society or others. *Do not list compensation*. We cannot know whether participation in KINDER will benefit participants directly, as we are still determining the evidence-base. However, it is possible caregivers will learn new information such as about local community resources.

HRP- 503SBER	TEMPLATE: CWR	U SBER Protoc	ol
Approved:	09/2021	Prior Version:	05/2021

23.0 Withdrawal of Research Participants

Directions: Describe the anticipated circumstances under which research participants will be withdrawn from the research without their consent. Also include the procedures that will be followed when a research participant withdraws or are withdrawn from the research, including partial withdrawal from procedures with continued data collection. Participants may be withdrawn from the study if they 1) do not complete the baseline survey or 2) miss 2 or more group-based sessions. Participants may continue to participate in the KINDER program if this occurs but will be removed from the study. If this does occur, the PI will send an email to the participant to notify them. We will keep all data collected until withdrawal unless asked not to by a participant. We will attempt to contact participants to learn about their reason for withdrawal. See "Call Scripts for Caregivers Who Go Off Protocol"

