
HRP- 503SBER	TEMPLATE: CWRU SBER Protocol		
Approved:	09/2021	Prior Version:	05/2021

recruitment include sharing flyers at community organizations and Facebook social media posts. Data Collection. Data collection will be primarily conducted in REDCap using self-administered surveys. A baseline survey will be sent within 2 weeks of the caregiver attending Discussion Session 1. The follow up survey will be sent immediately following completion of the intervention. Participants will receive up to 3 reminders to complete surveys. Caregivers who attend KINDER who do not participate in the study will also be invited to complete an anonymous satisfaction survey via REDCap. In addition to participant surveys, we will also ask facilitators, who are not members of the study team, to complete a facilitator monitoring report, call logs, and participant attendance forms to monitor adherence to protocols and intervention exposure. An observer from the study team will also complete a fidelity monitoring report using recorded discussion sessions. Some participants will also be asked to participate in a one-on-one semi-structured qualitative interview by phone or Zoom so we can learn more about experiences participating in KINDER. Participants will be purposefully selected, so as to ensure the representation of caregivers from various demographic backgrounds and caregiving situations. Further, we will send a satisfaction survey to all KINDER participants to learn more about their experiences participating in the program to support its ongoing improvement. For those who do not attend any or <2 discussion sessions, we will also send a survey asking about reasons for non-participation. Safety Monitoring. The PI will complete a safety monitoring report once every 3 months of this study. Information will include the number of individuals recruited, enrolled, dropped out, demographic information on participants, and descriptive information on study variables including the proportion of missing data for each variable.

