17.0 Data Analysis Plan

Directions: Describe the data analysis plan, including any statistical procedures. If applicable, provide a power analysis, and study/safety endpoints. Participant Demographic Characteristics Participant characteristics, including demographic and caregiving information (e.g., kin relationship) will be reported using frequencies, percentages, means, and standards of deviation. Comparison of Study and non-study participants.

Demographic characteristics of study and non-study participants collected from Eventbrite will be compared using t-test and chi-squared bivariate analyses, as well as frequencies and percentages. This will help the study team determine differences between caregivers who register for KINDER as a community program, and those who enroll in the study. Reasons for ineligibility and/or study or intervention withdrawal. The study team will also report the most frequent reasons for study or intervention withdrawal, as well as reasons participants were screened as ineligible, using frequencies and percentages. Outcomes. We will evaluate study outcomes using paired-t-tests comparing mean scores on all psychosocial outcomes collected before and after the intervention.

HRP- 503SBER	TEMPLATE: CWR	U SBER Protoc	ol
Approved:	09/2021	Prior Version:	05/2021

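### A discretionary attendance rule can remove a caregiver who has a baseline from the study at about the time the follow-up survey is due, and no analysis set is named, so the pre-post result may describe only retained caregivers

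*Combined protocol and SAP*

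**What the plan says.** Section 23.0 (Withdrawal of Research Participants) sets the rule: "Participants may be withdrawn from the study if they 1) do not complete the baseline survey or 2) miss 2 or more group-based sessions". Its consequence is: "Participants may continue to participate in the KINDER program if this occurs but will be removed from the study". On data, the section says: "We will keep all data collected until withdrawal unless asked not to by a participant". It then refers to a separate document, "Call Scripts for Caregivers Who Go Off Protocol", which is not among the documents reviewed.

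Section 12.0 (Data Collection) times the surveys. For baseline: "A baseline survey will be sent within 2 weeks of the caregiver attending Discussion Session 1". For follow-up: "The follow up survey will be sent immediately following completion of the intervention". Low attenders get a further questionnaire: "For those who do not attend any or <2 discussion sessions, we will also send a survey asking about reasons for non-participation". The schedule in section 3.0 puts the three discussion sessions in weeks 1, 5 and 9.

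Section 17.0 (Outcomes) gives the analysis: "We will evaluate study outcomes using paired-t-tests comparing mean scores on all psychosocial outcomes collected before and after the intervention". It names no analysis set and no method for missing follow-up. It does commit to tabulating reasons for withdrawal from the study or the intervention.

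**The concern.** This is a single-arm study, so mean change from baseline to follow-up is the only efficacy result for Aim 1. A paired t-test uses only caregivers with both surveys. The attendance rule acts after enrolment, on behaviour that may be related to benefit. It is worded as a permission, with no criteria for when it is used. A caregiver who was willing to complete the follow-up survey could therefore be left out by the study team's decision.

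If low attenders change less than others, the reported change is too favourable for everyone who started; if they change more, it is too low. Section 3.0 says the findings will inform later efficacy testing, so the group that the estimate describes matters.

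**Working it through.** **1. Who meets the rule, and when.** Write attendance at Sessions 1, 2 and 3 as 1 or 0. Missing two or more of three means attending at most one, which gives four patterns:

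| Pattern | Second miss | Attended Session 1, so baseline clearly due? |
|---|---|---|
| 000 | week 5 | no |
| 001 | week 5 | no |
| 010 | week 9 | no |
| 100 | week 9 | yes |

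Only pattern 100 clearly has a baseline. For the other three, the plan does not say whether a baseline survey is sent to someone who misses Session 1.

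**2. Order of events for pattern 100.** The rule is met in week 9, the last week of the programme. The follow-up survey is tied to completing the intervention, so it falls due at about the same time. The plan does not say which comes first, and the trigger is not defined for someone who does not complete.

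**3. The plan's own figures.** Section 5.0 plans 46 enrolled to reach 34, a difference of 12 (12/46 = 26%) with no stated cause. The 34 is used below only as the number analysed. As a separate matter, taking a medium effect as 0.5 SD (my assumption), the stated one-sided test at alpha 0.05 and power 0.80 needs 27; 34 matches a two-sided test (power 0.808).

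**4. Size, as an illustration.** Only the 34 comes from the plan. Assume the 34 retained improve by 0.50 SD of the change score, and that k removed caregivers with a baseline would have changed by c.

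Mean over all with a baseline = (34 × 0.50 + k × c) / (34 + k).

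| c (SD) | k = 2 | k = 4 | k = 6 | Reported 0.50 is |
|---|---|---|---|---|
| 0 | 17/36 = 0.472 | 17/38 = 0.447 | 17/40 = 0.425 | 6%, 12%, 18% too high |
| 0.25 | 0.486 | 0.474 | 0.463 | 3%, 6%, 8% too high |
| 0.50 | 0.500 | 0.500 | 0.500 | correct |
| 0.75 | 0.514 | 0.526 | 0.538 | 3%, 5%, 7% too low |

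For c = 0 the difference is 0.028, 0.053 or 0.075 SD. The standard error with 34 analysed is 1/√34 = 0.171 SD, so the difference is 0.16 to 0.44 of a standard error.

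**5. Effect on the test when nothing changes.** Suppose true mean change is zero, the tendency to attend correlates r with change, and the lowest fraction p = k/(34 + k) is removed. The retained mean shifts by r × φ(z)/(1 − p), with z = Φ⁻¹(p). For r = 0.2 the shift is 0.024, 0.041 or 0.055 SD for k = 2, 4 or 6. The one-sided 5% test with 33 degrees of freedom then rejects 6.6%, 7.9% or 9.2% of the time. For r = −0.2 it rejects 3.7%, 3.0% or 2.5%. The value of r is also an assumption.

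**The case against.** Change among caregivers who take part is a defensible target for a pilot. Section 12.0 describes participation as including the full 9-week intervention and both surveys, and Aim 1 speaks of change following participation. Together these lean towards a completer target. That stands as a leaning, but no section states it as the analysis set. Section 17.0 also does not limit the t-tests to attenders, so a low attender who is not removed and has both surveys would be included.

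The group clearly affected is narrow, removal is optional, and the sentence on keeping data does not forbid a later survey. The off-protocol call scripts might cover follow-up. All of this stands, and it is why the loss is possible and not certain. Reporting withdrawal reasons would show readers that caregivers were removed. It would not supply their outcomes, and neither would the reasons survey.

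Three stronger readings are tempting:

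- **The efficacy result will be inflated.** The documents give no relation between attendance and change, so neither direction nor size is fixed.
- **The 12-caregiver gap between 46 and 34 is caused by this rule.** The plan gives no cause for it.
- **Every caregiver who meets the rule loses an outcome.** Only the Session 1 only pattern clearly has a baseline to pair.

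**Conclusion.** The point holds in a limited form and should be fixed. The plan contains a rule that can remove enrolled caregivers from outcome collection because of low attendance, applied at the team's discretion, with no provision for later follow-up and no named analysis set. If it is applied, the paired t-tests describe retained caregivers only.

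The likely effect is modest. In the illustration with 2 to 6 removed caregivers who do not change, the reported mean is 0.03 to 0.075 SD too high, less than half a standard error. It vanishes if they change as much as the others and reverses if they change more. These figures rest on an assumed number removed, an assumed 0.50 SD among those retained and assumed changes in those removed. The gap in the text does not depend on them.

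**What to change.** - **Section 23.0:** stop using missed sessions as a reason to end data collection. Record low attendance only as a matter of intervention participation; section 15.0 already collects that reason separately from study withdrawal. Access to KINDER is unchanged.
- **Section 12.0:** send the follow-up survey at the end of the 9-week programme to every caregiver with a baseline survey, whatever their attendance, unless they withdraw consent. State whether a caregiver who misses Session 1 is sent a baseline survey.
- **Section 17.0:** define the primary paired analysis as all caregivers with both surveys regardless of attendance. Report how many with a baseline lack follow-up. Give caregivers who attended at least two sessions as a labelled secondary analysis. A simple sensitivity analysis for missing follow-up is optional; multiple imputation as the primary method is not needed for a pilot of this size.

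The cost is a short amendment and $75 per extra survey under section 26.0: 2 × $75 = $150 to 6 × $75 = $450 in the illustrated range. Section 12.0 already plans to contact those attending fewer than two sessions. The estimate may be less favourable, and some low attenders will still not respond.

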24.0 Alternatives to Participation

Directions: List other options to participation. If subjects will be compensated with extra course credit, the course instructor offering extra course credit must provide alternatives to earn extra course credit. The alternative assignment must require equal or less time and effort for the same amount of earned extra credit that you can earn through participation in research. If there are other available clinical treatments, what would be included if a subject continued on standard of care therapy. If there is a viable alternative you must list it in the consent.

Click here to enter text.

☑ The alternative is for research subjects not to participate.

25.0 Costs to Research Participants

- ☑ There are no costs to research participants or their insurance companies (there are no clinical visits or billable procedures.) *please leave rest of this section blank*
- 1. Describe what costs research participants will be responsible for as a result of their participation in the research, including but not limited to: clinical services required by the protocol deemed billable to insurance, transportation to study visits, parking, costs of drugs, cost of therapy, lost broken or stolen devices, etc. Click here to enter text.
- 2. Explain who will be responsible for payment of provided services in the event of insurance denials. Click here to enter text.
- 3. List what procedures, drugs, devices, supplies will be paid by the study sponsor or covered by other funding. List the other funding source. Click here to enter text.

